15.1 Control of data consistency

Data forms will be entered in the database of the EORTC Data Center either by a double data entry procedure or by using the RDC system. Sites will be asked to choose one of both options at the start of the study. Computerized and manual consistency checks will be performed on newly entered forms; queries will be issued in case of inconsistencies. Consistent forms will be validated by the Data Manager to be entered on the master database. Inconsistent forms will be kept "pending" until resolution of the inconsistencies.

15.2 Audits

To ensure quality of data, study integrity and compliance with the protocol and the various applicable regulations and guidelines, the EORTC Quality Assurance Unit regularly conducts site visits to institutions participating in EORTC protocols.

The investigator, by accepting to participate in this protocol, agrees to co-operate fully with any quality assurance visit undertaken by authorised third parties, including representatives from EORTC, national and/or foreign regulatory authorities.

The investigator will also grant direct access to documentation pertaining to the clinical trial (including CRF, source documents, hospital patient charts and other study files) to these authorized individuals.

The investigator must inform the EORTC Data Center immediately in case a regulatory authority inspection is scheduled.

15.3 External review of histology

Histological classification and grading of the meningioma must be assessed for all patients by the local pathologist prior to entry on study.

Central pathology review will be performed by the central neuropathologists after patient inclusion.

After each patient inclusion, please send immediately:

- ◆ Copy of the pathology report (anonymous, indicate patient SeqId)
 - ◆ results of progesterone and estrogen receptor immunohistochemistry (if available)
 - ◆ mitotic index (in the pathology report)
- ◆ Copy of the operative (surgery) report (anonymous, indicate patient SeqId)
- ◆ 1-2 representative H&E sections
- ◆ 15-20 unstained slides from each block suitable for immunohistochemistry
- ◆ Paraffin embedded tumor material (strongly encouraged, not mandatory)
- ◆ Notify whether fresh-frozen tumor tissue is available (strongly encouraged, not mandatory) and where it is located – to be send on request.

To be sent for central pathology review at:

[name]
 Attn: [name], Neuropathologist
 ERASMUS UNIVERSITY MEDICAL CENTER
 [name]
 [name]
 The Netherlands

(All EORTC-trial related materials are sent to [name]'s administration prior to sending on to [name]).

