counts can be achieved after embolization (Ref. 17). This criterion was also a major prognostic factor in other series (Ref. 10, Ref. 12, Ref. 18, Ref. 19). As a result, this maximal mitotic rate alone (≥ 4 mitosis per high-power field [HPF]) usually allows a diagnosis of atypia in the absence of other features, such as increased cellularity, architectural sheeting (i.e. patternless pattern), macronuclei and small cell formation (Ref. 20). Likewise, the presence of at least 3 of the latter 4 variables was associated with a statistically significant decreased progression-free survival in the Mayo study (Ref. 16). As a result, in the absence of aforementioned maximal mitotic rate, the diagnosis of atypia can be made also if at least three of these four features are present. Tumors are usually classified as malignant if they have either of the following criteria: (1) excessive mitotic rate (≥ 20 HPF), or (2) dedifferentiation or frank anaplasia on light microscopy. Even with these strict histological criteria, a correct histopathological diagnosis cannot be made in a substantial number of cases ($\approx 15\%$) (Ref. 21).

Finally, most series have reported a strong association between histological grade and gender, with male presenting more frequently with non-benign meningioma (roughly 3 – 4 times) than females (Ref. 13, Ref. 16), while others have observed an equal male/female ratio (Ref. 14, Ref. 15).

The significance of brain invasion is somewhat controversial (Ref. 22). Moreover, this criteria is difficult to evaluate as in most cases, brain parenchyma is lacking or is unsampled. Simple perivascular extension along Virchow-Robin spaces is usually not considered as brain invasion, whereas finger-like or knobby protrusions into underlying cerebral or cerebellar cortex are considered a characteristic of brain invasiveness. This invasiveness commonly produces a gliotic reaction. In the Mayo series, brain invasion was strongly associated with decreased recurrence-free survival on multivariate analysis (Ref. 16). Although this criterion was adversely associated with outcome in several series (Ref. 16), it has not been assessed in other large clinical series (Ref. 11, Ref. 12, Ref. 13, Ref. 14, Ref. 15). Currently, brain invasion is not a criterion *per se* for the grading of meningiomas in the new WHO classification (Ref. 1).

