8.1 Statistical design

8.1.1 Sample size

For patients with atypical meningioma (grade II) the trial is designed as two parallel non-randomized phase-II trials with progression-free survival rate at 3-years as primary endpoint.

The trial is therefore stratified in two groups: the patients with Simpson's stage 1-3 resection and patients with Simpson's stage 4-5 resection.

A separate one-stage Fleming design (Ref. 101) will be applied each to the two strata of patients with WHO grade II disease. The criteria for success are respectively to demonstrate that the 3-year progression free survival is superior to 70% for patients with Simpson's stage 1-3 and that it is superior to 50% for patients with Simpson's stage 4-5.

With such a design, a total of 25 patients with Simpson stage 1-3 grade II meningiomas and 39 patients with Simpson stage 4-5 meningiomas **eligible and starting treatment** are needed (total phase II study, 64 patients).

For the grade III meningiomas, given the small numbers expected to enter the trial, the patients will only be followed-up similarly to the grade II meningiomas. No specific statistical design, no decision rule and no sample size are defined for this small group. Only descriptive statistics will be produced. The trial duration will be driven by the phase II study. It is foreseen that 6-13 grade-III patients will be registered during the accrual period of the phase II.

Accrual to the phase II is anticipated to last 3 years.

All patients need to be followed for a minimum of 3 years or until death or progression of the disease. Ineligible patients and those who do not start treatment need to be replaced in the sample.

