8.2.2 Analysis populations

- ◆ Intention-to-treat population: all patients entered in the study
- ◆ Per protocol population: all patients who are eligible and have started the planned treatment (at least one fraction of irradiation)
- ◆ Safety population: all patients who have started the planned treatment (at least one fraction of irradiation)

A patient will be considered to be eligible if he/she did not have any major deviations from the patient entry criteria listed in chapter 3 of the protocol. Eligibility will be assessed by the Study Coordinator based on the review of each patient file.

For eligibility and stratification (WHO II vs WHO III), the histology assessed by the local pathologist will be considered.

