8.2.4 Pre-planned sensitivity or exploratory analyses

Sensitivity analyses will be performed according to the central pathology review. The efficacy endpoints will be analyzed in the populations that are defined as in 8.2.2 but considering the eligibility and the allocation to strata in the trial in function of the central pathology review assessment.

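### Central pathology review gets the local report with the slides and no reading order is set, so the central grade used in the 8.2.4 sensitivity analysis may lean toward the local grade

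*Protocol*

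**What the plan says.** Section 15.3 of the protocol places the local reading first: "Histological classification and grading of the meningioma must be assessed for all patients by the local pathologist prior to entry on study". The central reading follows: "Central pathology review will be performed by the central neuropathologists after patient inclusion". One list then sets out what the site sends for that review. It includes "Copy of the pathology report (anonymous, indicate patient SeqId"), with "mitotic index (in the pathology report") named as an item, along with the operative report, one or two H&E sections and 15-20 unstained slides per block. All of it goes first to an administration, which passes it on to the neuropathologist. That administration is given no masking task.

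The two grades have different uses. Under section 8.2.2, "For eligibility and stratification (WHO II vs WHO III), the histology assessed by the local pathologist will be considered". The central grade enters in section 8.2.4: "Sensitivity analyses will be performed according to the central pathology review". There the efficacy endpoints are re-analysed with eligibility and stratum taken from the central assessment.

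Section 1.1 warns that even under strict criteria "a correct histopathological diagnosis cannot be made in a substantial number of cases", and puts the share at about 15%.

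**The concern.** The second reading is useful because it can disagree with the first. If the central neuropathologist reads the local grade and mitotic count before looking at the slides, a borderline case may be settled in favour of the local call.

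The protocol gives reason to expect borderline cases. A mitotic count alone can establish grade II, and the criteria are not uniform across the document. Section 1.1 gives the threshold of 4 mitoses once per 10 high-power fields and once per high-power field, and section 3 uses the latter. Section 3 asks for three of four further features, while section 3.1 asks for three or more from a list of five.

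What is at stake is how far the sensitivity analysis can be trusted. If it agrees with the primary result, that could mean misgrading is rare, or only that the central reader followed the local report. As section 15.3 stands, the two explanations could not be told apart.

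**Working it through.** **1. Does the point touch the design?** Section 8.1.1 requires "a total of 25 patients with Simpson stage 1-3 grade II meningiomas and 39 patients with Simpson stage 4-5 meningiomas". Exact binomial calculation reproduces the stated error rates:

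- n = 25, success at 21 or more progression-free: P(X ≥ 21 | 0.70) = 0.0905 and P(X < 21 | 0.90) = 0.0980. The protocol states 0.09 and 0.098.
- n = 39, success at 24 or more: P(X ≥ 24 | 0.50) = 0.0998 and P(X < 24 | 0.70) = 0.0944. The protocol states 0.10 and 0.094.

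Both are the smallest n with both errors at or below 10%. The cut-offs 21 and 24 are those that reproduce the stated errors; the protocol's operative rule is the lower Kaplan-Meier confidence bound. Neither rule uses the central grade, so nothing here changes.

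**2. Is the central reader kept unaware of the local grade?** Section 15.3 has the local grade fixed before entry, the report and mitotic index sent with the slides, and the review done after inclusion. The identifier on the report is the SeqId, so anonymity concerns the patient. No section says that the grade is removed, that the report is held back, or that the central grade is recorded before the report is opened. Independence is therefore not secured. Nor does the protocol say that the reader opens the report first.

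**3. Is there another check on misgrading?** Section 8.2.4 is the only planned analysis that takes up the question. Section 8.2.5 plans no prognostic-factor analysis, and section 8.2.2 fixes the local grade for everything else.

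**4. Can the effect be sized?** Take one direction only: locally graded II tumours that are truly lower grade. Let m be their share, a the share of them the central reader leaves as grade II, q their 3-year PFS and P0 the rate in the rest. Then

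- residual misgraded share r = m·a / (1 − m + m·a)
- shift in the sensitivity estimate = r × (q − P0)

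The protocol gives none of m, a and q. Its 15% is general diagnostic uncertainty, with no direction and no local-versus-central comparison. Purely as assumptions, take m = 0.15, a = 0.5 and q = 0.90 to 0.95. Then r = 0.075/0.925 = 0.081. The shift is 0.081 × (0.20 to 0.25) = 1.6 to 2.0 points at P0 = 70%, and 0.081 × (0.40 to 0.45) = 3.2 to 3.6 points at P0 = 50%.

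Letting m run from 0.05 to 0.25 and a from 0 to 1 gives 0 to 0.25 × 0.25 = 6.25 points and 0 to 0.25 × 0.45 = 11.25 points. Unrecognised grade III tumours would push the other way if their PFS is lower, and they are not in this sum. The range reflects the assumptions, so it is not an estimate.

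**5. How does that compare with the precision?** One binomial standard error is √(0.70 × 0.30/25) = 9.2 points at n = 25 and √(0.50 × 0.50/39) = 8.0 points at n = 39. The middle illustration is under half of either.

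**6. What can masking hide?** Only grade II or III cases are registered, so the reader knows that every case was called non-benign locally. With 64 grade II and 6 to 13 grade III patients planned, 64/77 = 83% to 64/70 = 91% are local grade II. Holding the report back hides the local mitotic count, the features described and the II-versus-III call, but not the rejection of grade I.

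**The case against.** A reader might infer that the central grade is not independent and that the sensitivity analysis is biased toward agreement. The documents do not support stating either as fact. Section 15.3 is a shipping list and does not say when the report is opened. The reader also has sections and unstained slides from which to grade afresh. Section 10.3 mentions EORTC rules for central pathology review that are not reproduced in the protocol, and these might set a reading order. This stands as a reason to write of a risk. It does not show that masking is in place.

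A reader might also carry the 15% into the decision strata and conclude that the chance of a false success exceeds the stated 9% and 10%. That does not follow. Any such effect would come from misgrading in the primary analysis, which uses the local grade by choice, and masking the central reader would not alter it. Nor is the 15% a misgrading rate, and no decision rule is attached to section 8.2.4.

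Two practical objections also stand. Masking is partial, as step 6 shows. And the atypia criterion in section 1.1 rests on a maximal mitotic rate, while the site sends only one or two H&E sections and unstained slides meant for immunohistochemistry. A grade fixed before the report is read may therefore differ from the local one because of sampling, not error.

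**Conclusion.** The point holds as a risk. The local report, carrying the local grade and mitotic index, goes to central review with the slides, and no masking or reading order is stated. The central grade used in section 8.2.4 may therefore be drawn toward the local grade, and the analysis may understate misgrading. The size, and with grade III contamination even the net direction of the effect on PFS, cannot be derived from the protocol. The figures in step 4 illustrate scale under stated assumptions and are not findings.

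The primary analysis, the decision rule and the sample size are unaffected. Severity is low. It is still worth acting on, because this is the only planned look at misgrading and the remedy costs little.

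**What to change.** In section 15.3, state that the receiving administration holds the local pathology report, including the mitotic index, until the central neuropathologist has recorded WHO grade and mitotic count from the slides under the SeqId. The report is then released, and any revised central grade is recorded separately. In section 8.2.4, state that the grade recorded first is the one used, and that local-central discordance will be reported. Keeping the revised grade as a second field lets disagreement due to limited sections be told apart from disagreement in judgement.

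The cost is a few sentences, one handling step in an administration that already exists, and a short delay before the reviewer sees the report. No patient, slide or reader is added, and no sample-size figure changes. Some discordance may arise from the limited sections sent, and the reader will still know that each case was called grade II or III locally.

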15.4 Quality assurance of radiotherapy

The quality assurance for radiotherapy in this study will be done jointly with *Advanced Technology Radiation Therapy Clinical Trials* and Advanced Technology Consortium network (ATC).

Therefore this trial has specific requirements to assess and ensure the quality of the radiotherapy delivered to every patient. The procedures will be performed via the web and will use only electronic data (DICOM-RT) and image files (format jpg, bitmap, etc).

The objectives are to check compliance with the protocol guidelines regarding PTV definition, planning technique and clinical and technical documentation. This includes image co-registration and treatment verification procedures.

The main responsible person for the QA is the Study Coordinator with the help of EORTC ROG QA team and ROG coordinating physician and in collaboration with the ATC team,

The following three steps are mandatory:

1. All centers must fill in the Facility Questionnaire prior to the first patient entry.
2. Before the center is allowed to randomize patients, it should show that the protocol is well understood and that the center is able to treat patients according to the specified guidelines. Therefore a first patient case check is mandatory for each center and must be done prior to the randomization.
 - ◆ **For the Demonstration of Digital Data Submission Capability Test:** please contact the EORTC ([contact]) and request an ATC FTP account for digital data submission. You have to submit a complete patient digital data set to demonstrate compliance with 3D/IMRT technical requirements.
 - ◆ **Timely Review by EORTC-ATC:** A timely review of the first submitted protocol case that an institution registers will be performed. The timely review will not hold up the patient treatment as it must be completed within the first 5 days after data has been received by EORTC-ATC.
3. The individual cases review will check the data for all patient(s) entered in the trial.

The following information is to be submitted for each patient:

- ◆ Digital Data Submission Information Form (DDSI Form obtain from ATC website).
- ◆ Treatment prescription and verification images
- ◆ Protocol compliant images (e.g. CT or MRI scan series);
- ◆ Protocol compliant contours using required standard names (standard structure names can be found on the ATC website) for all GTV, CTV and PTVs, and for all specified critical normal

structures. They must be contoured on all slices in which each structure exists or as defined by the protocol and include skin on ALL CT cuts;

- ◆ Color 2D isodose distribution plots for the axial, sagittal and coronal planes through the isocenter for the total dose plan must be submitted. They may be electronic files of screen dumps, such as jpg or bmp files. Volumetric 3-D dose distribution (**with** heterogeneity corrections) data in absolute dose for each fraction group used to deliver a protocol compliant dose. Note, a Fraction Group represents the beams and doses for a concurrently treated set of beams;
- ◆ DVH's computed **with** heterogeneity correction for the total dose of all dose distributions submitted for item c (summed fraction groups from item c) for all PTVs and all specified critical normal structures. A DVH of all “unspecified tissue” must also be provided.

In case some centers are unable to upload data to their server (because of software compatibility), we will provide a list of the TPS that are compatible with the ATC system.

16 Ethical considerations

16.1 Patient protection

The responsible investigator will ensure that this study is conducted in agreement with either the Declaration of Helsinki (Tokyo, Venice, Hong Kong, Somerset West and Edinburgh amendments) and/or the laws and regulations of the country, whichever provides the greatest protection of the patient.

The protocol has been written, and the study will be conducted according to the ICH Harmonized Tripartite Guideline on Good Clinical Practice (ICH-GCP, available online at <http://www.emea.eu.int/pdfs/human/ich/013595en.pdf>).

The protocol must be approved by the competent ethics committee(s) as required by the applicable national legislation.

16.2 Subject identification

The name of the patient will neither be asked for nor recorded at the EORTC Data Center. A sequential identification number will be automatically allocated to each patient registered in the trial. This number will identify the patient and must be included on all case report forms. In order to avoid identification errors, the patient's code (maximum of 4 letters), date of birth and local chart number (if available) will also be reported on the case report forms.

16.3 Informed consent

All patients will be informed about

- ◆ the aims of the study
- ◆ the possible adverse events
- ◆ the procedures and possible hazards to which the patient will be exposed
- ◆ the mechanism of treatment allocation
- ◆ strict confidentiality of any patient data

- ◆ medical records possibly being reviewed for trial purposes by authorized individuals other than their treating physician.

The template of the patient's informed consent statement is given as an appendix to this protocol.

It is the responsibility of the Coordinating Investigators for this trial (sometimes called National Coordinators) to translate the enclosed informed consent document. The translated version should be dated and version controlled.

The bold sections of the informed consent document must be reflected in any translation. The content of these bold sections can either be translated literally or translated in any way that best captures the information given.

The translated informed consent documents are to be submitted to ethics committees for approval. The competent ethics committee for each institution must approve the informed consent documents before the center can join the study. It is the responsibility of the competent ethics committee to ensure that the translated informed documents comply with ICH-GCP guidelines and all applicable national legislation.

It is emphasized in the patient information sheet that participation is voluntary and that the patient is free to refuse further participation in the protocol whenever he/she wants to. This will not have any impact on the patient's subsequent care. Documented informed consent must be obtained for all patients included in the study before they are registered and/or randomized at the EORTC Data Center. The written informed consent form must be signed and personally dated by the patient or by the patient's legally acceptable representative".

All of the above must be done in accordance with the applicable national legislation and local regulatory requirements.

17 Administrative responsibilities

Authors of the manuscript will include at least the Study Coordinator, the investigators who have included more than 5% of the eligible patients in the trial (by order of inclusion), and a minimum of two members of the Data Center team who have contributed to the trial.

The title of all manuscripts will include “EORTC”, and all manuscripts will include an appropriate acknowledgment section, mentioning all investigators who have contributed to the trial, the data center staff involved in the study, as well as supporting bodies (NCI, cancer leagues, sponsors...).

All publications (papers, abstracts, presentations...) including data from the present trial will be submitted for review to the Data Center and to all co-authors prior to submission.

The Group Chairman, the Study Coordinator and the Data Center Team must approve all publications, abstracts and presentations of data pertaining to patients included in this study.

This is applicable to any individual patient registered in the trial, or any subgroup of these. Such publications must comply with the terms specified in the EORTC Policy 009 “Release of Results and Publication Policy”. Therefore, such a publication cannot include the analysis of any of the study end-points unless the final results of the trial have already been published by the Study Coordinator.

It is the EORTC's policy not to release trial results before data maturity has been reached for the primary endpoint(s) of the trial unless the publication is authorized by an Independent Data Monitoring Committee. If the group wishes to publish or present study data before the publication of the primary trial endpoint, this may be authorized under the conditions specified in the EORTC Policy 009 "Release of Results and Authorship Policy" available from <http://www.eortc.be>, or authorized by an Independent Data Monitoring Committee.

